3.7.2. Deaths, Serious and Other Significant Adverse Events

The number and percentage of subjects with at least one SAE (regardless treatment emergent or not) will be summarized by SOC and PT for the Safety Population. Deaths and AEs leading to discontinuation (regardless treatment emergent or not) will be summarized similarly.

Supporting listings of serious AEs and AEs leading to study discontinuations will be provided. Subjects who died during the study will also be listed.

3.7.3. Adverse Events of Special Interest

Adverse events in the following categories of interest will be presented by following categories and PTs:

- Anaphylaxis and Angioedema (serious adverse events)
- Lymphopenia
- Liver Injury
- Malignancies and Pre-malignant Conditions
- Opportunistic Infections (AEs and SAEs) and All Serious Infections (Including Opportunistic Infections SAEs)
- Pancreatitis

- Renal Injury
- Cardiac Disorders
- Gastrointestinal Tolerability AEs (serious adverse events and adverse events leading to discontinuation)
- Abuse potential

Supportive AE listings including serious and non-serious AEs will be provided for each special interest group. Additionally, listing for “non-specific” AEs in the abuse potential category will be provided. Narratives will be provided for “euphoria related” and “abuse behavior” AEs in the category of abuse potential.

3.7.4. Clinical Laboratory Parameters

Laboratory parameters will be presented in conventional units. Only scheduled laboratory parameters will be included in the summaries of laboratory data. All laboratory data, including those collected at unscheduled visits, will be included in the listings. Laboratory results (baseline and change from baseline) for chemistry, hematology and urinalysis parameters for each visit during the entire study will be summarized by treatment group and overall.

For urinalysis, the number of abnormalities at any post-baseline visit will be summarized. In addition, the number and percentage of subjects with values considered potentially clinically significant (PCS) occurring at any post-baseline visit for selected parameters will be summarized by treatment group and overall.

Clinical laboratory test values, scheduled or unscheduled during the treatment period, will be considered PCS if they meet the PCS criteria listed in [Table 2](#). The percentages will be calculated relative to the number of subjects with available non-PCS baseline values with respect to the specific criterion and at least 1 post-baseline assessment. The denominator is the total number of subjects with a non-PCS baseline value with respect to the specific criterion and at least 1 postbaseline PCS value. A supportive listing will present all values for a parameter for subjects with at least one PCS value for that parameter.

Shift tables for shift from within normal reference limits / high to low and shift from within normal reference limits / low to high during the treatment period will be provided for chemistry and hematology parameters with conventional reference limits (limits provided by the performing laboratories) by treatment group and overall for the Safety Population. For parameters which have gender and / or age specific limits, the categories will be based on the specific limits. High is defined as values greater than the upper limit of the reference range (ULRR). Low is defined as values less than the lower limit of the reference range (LLRR). Normal reference limits is defined as values within normal range.

The percentages will be calculated for the shift summary as follows:

- For the shifts from within normal reference limits / high to low: the numerator is defined as the number of subjects with a post-baseline result below the LLRR, and the denominator is defined as the number of subjects with a baseline value within the limits or above the ULRR.

- For the shifts from within normal reference limits / low to high: the numerator is defined as the number of subjects with a post-baseline result above the ULRR, and the denominator is defined as the number of subjects with a baseline value within the limits or below the LLRR.

The following figures will be presented by treatment group and overall:

- Mean along with the corresponding SE for change from baseline values for selected chemistry and hematology laboratory parameters.
- Boxplots will be used to display summary statistics for the maximum and minimum change from baseline values for selected chemistry and hematology laboratory parameters.

Pregnancy test data will be listed.

Table 2: Potentially Clinically Significant (PCS) Criteria for Laboratory Parameters

Category	Parameter	Criteria
Hematology	Hematocrit	$\leq 32\%$ and 3 point decrease from baseline (Female) $\leq 37\%$ and 3 point decrease from baseline (Male)
	Hemoglobin	$\leq 9.5 \text{ g/dL}$ (Female) $\leq 11.5 \text{ g/dL}$ (Male)
	Neutrophils	$< 1.5 \times 10^3/\mu\text{L}$
	Platelets	$< 75.1 \times 10^3/\mu\text{L}$ $\geq 700 \times 10^3/\mu\text{L}$
	WBCs -total, differential (absolute)	$\leq 2.8 \times 10^3/\mu\text{L}$ $\geq 16 \times 10^3/\mu\text{L}$
	Eosinophils	$> 1.0 \times 10^3 \text{ cells}/\mu\text{L}$
	Lymphocytes	$< 0.5 \times 10^9/\text{L}$
Chemistry	ALT	$\geq 3 \times \text{ULN}$
	Albumin	$< 2.5 \text{ g/dL}$
	ALK-P	$\geq 3 \times \text{ULN}$
	AST	$\geq 3 \times \text{ULN}$
	Bicarbonate	$< 15 \text{ mmol/L}$ $> 31 \text{ mmol/L}$
	BUN	$> 30 \text{ mg/dL}$
	Calcium	$< 8.2 \text{ mg/dL}$ $> 12 \text{ mg/dL}$
	Chloride	$\leq 90 \text{ mmol/L}$ $\geq 118 \text{ mmol/L}$
	Creatine Kinase	$> 3 \times \text{ULN}$

Category	Parameter	Criteria
	Creatinine	≥ 2 mg/dL
	Glucose	< 50 mg/dL > 200 mg/dL
	HDL Cholesterol	≤ 30 mg/dL
	Lactate Dehydrogenase	$>3 \times$ ULN
	LDL Cholesterol	≥ 160 mg/dL
	Phosphorus	<2 mg/dL >5 mg/dL
	Potassium	<3 mmol/L >5.5 mmol/L
	Sodium	<130 mmol/L >150 mmol/L
	Total Bilirubin	≥ 2 mg/dL
	Total Cholesterol	>300 mg/dL
	Triglycerides	≥ 120 mg/dL (Female) ≥ 160 mg/dL (Male)
	Uric Acid	> 9 mg/dL > 8 mg/dL (Female) > 10 mg/dL (Male)
Urinalysis	Glucose	at least 2+
	Protein	at least 2+
	Albumin/Creatinine	>200 g/kg
	Beta-2 Microglobulin	>0.300 mg/L

For abnormal liver function tests, the number and percentage of subjects will be summarized by upper limit of normal (ULN) category as follows:

- ALT (alanine aminotransferase), AST (aspartate aminotransferase) and ALK-P (alkaline phosphatase) will be summarized by normal, >3 xULN, >5 xULN, >10 xULN, total bilirubin by >1.5 xULN and >2 xULN.

Number of subjects who meet Hy's Law criteria (total Bilirubin ≥ 2 xULN and ALT or AST ≥ 3 xULN) will be summarized and corresponding listing will be presented.

Number of Subjects with Lymphopenia by Maximum NCI-CTCAE Toxicity Grade 1-4 will be summarized. Subjects with Lymphopenia Toxicity Grade 2 or higher will also be listed.

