3. DATA ANALYSIS

3.1. General Statistical Methodology

The safety and efficacy endpoints will be summarized by treatment group and overall as described below. In general, summary statistics (n, mean, standard deviation [SD], median, minimum, and maximum for continuous variables, and number and percentage of subjects in each category for categorical variables) will be provided by treatment group and overall. All summary tables will be based on observed data, and missing values will not be imputed unless otherwise indicated. Measurements collected from unscheduled visits or repeated assessments will not be included in the by-visit summary tables or figures, but will be included in the analyses for the potentially clinically significant (PCS) post-baseline values and subject listings. Source data for the summary tables and statistical analyses will be presented as by-subject data listings.

Baseline value is defined as the last non-missing assessment prior to the first dose of study drug.

All statistical tests and confidence intervals (CIs), unless stated otherwise, will be 2-sided and will be set at an alpha level of 0.05.

All the efficacy analyses will be summarized by the planned treatment assignment, and all the safety analyses will be summarized by actual treatment.

The data will be summarized for the following two study periods as appropriate.

- Treatment Period, which is defined as the period between the first dose date after randomization and the last dose date plus 1 day, inclusive.
- Follow-up Period, which is defined as the period between the date of the last dose date plus 2 day and the last study date, inclusive.

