6.1. Analysis Visit Windows

Scheduled analysis visits are visits upon scheduled time points as specified in [Table 1 Schedule of Visits and Assessments](#).

Scheduled analysis visits during the study period will be the same as the nominal visits collected in the eCRF. There will be one valid value of the assessment kept for each scheduled analysis visit in summary/ analysis statistics.

Unscheduled visits are visits with data not collected on the scheduled time point. Unscheduled visits will not be used for by-visit summary/analysis statistics unless specified otherwise. All unscheduled visits will be included as collected in eCRF in listings.

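### Section 3.7.4 limits laboratory summaries to scheduled values with an exception only for PCS, so the Hy's Law, ULN-category, lymphopenia-grade, shift and maximum/minimum-change outputs could miss a peak or nadir seen at an unscheduled draw

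*SAP*

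**What the plan says.** SAP Section 3.7.4 sets the rule for laboratory data: "Only scheduled laboratory parameters will be included in the summaries of laboratory data". The next sentence tells where the rest goes: "All laboratory data, including those collected at unscheduled visits, will be included in the listings". The section then makes one exception. For PCS, "Clinical laboratory test values, scheduled or unscheduled during the treatment period, will be considered PCS if they meet the PCS criteria", and the result is itself a summary, with counts and percentages of values "potentially clinically significant (PCS) occurring at any post-baseline visit for selected parameters will be summarized by treatment group and overall".

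The same section plans further outputs without saying which samples feed them: shift tables, boxplots of maximum and minimum change from baseline, ALT, AST, ALK-P and bilirubin by multiple of ULN, the "Number of subjects who meet Hy's Law criteria", and a lymphopenia table ("Number of Subjects with Lymphopenia by Maximum NCI-CTCAE Toxicity Grade 1-4 will be summarized").

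The general sections are worded more narrowly. Section 3.1: "Measurements collected from unscheduled visits or repeated assessments will not be included in the by-visit summary tables or figures". Section 6.1: "Unscheduled visits will not be used for by-visit summary/analysis statistics unless specified otherwise". Section 7 repeats the rule of Section 3.1, and adds the last post-baseline value on treatment to the uses for which unscheduled results are kept.

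**The concern.** The outputs in question report a subject's extreme, or any post-baseline excursion. They serve their purpose only if they see every available value. Under the literal rule of Section 3.7.4 they would see scheduled samples alone.

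Two things are at stake.

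- **Safety counts.** Liver injury and lymphopenia are named events of special interest in Section 3.7.3. Table 1 lost part of its column structure in extraction, but it appears to place post-baseline chemistry and hematology only at Visit 5, Visit 8 (ET) and Visit 9. By Section 1.2, subjects who roll over into the long-term study do not have Visit 9. With so few planned draws, an extreme can fall between them. Any error from the filter is in one direction, towards fewer abnormal subjects.
- **Reproducibility.** A programmer who follows Section 3.7.4 would filter to scheduled records. One who follows Section 3.1 could keep every record. The same table could then show different counts depending on which section was read.

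**Working it through.** No sample size, power or event figure is involved, so the check is a comparison of the sections.

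**Step 1: scope of the rule.** The sentence in Section 3.7.4 covers summaries of laboratory data and carries no by-visit limit. Sections 3.1, 6.1 and 7 attach their exclusion to by-visit statistics. Because Section 3.7.4 writes out an exception for PCS, the natural reading is that its rule governs laboratory outputs that have no exception.

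**Step 2: outputs that are not by-visit.**

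| Output (Section 3.7.4) | By-visit? | Express inclusion of unscheduled values? |
|---|---|---|
| PCS counts | No | Yes, treatment period |
| Shift tables | No, any post-baseline result | No |
| Maximum/minimum-change boxplots | No, subject extreme | No |
| ULN categories | No | No |
| Hy's Law count | No | No |
| Maximum lymphopenia grade | No, subject extreme | No |

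One of the six has an exception and five do not. For those five, Section 3.7.4 read literally excludes unscheduled values, while the by-visit exclusion in Sections 3.1, 6.1 and 7 does not reach them.

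**Step 3: does PCS replace the five?** Table 2 sets PCS at ≥3×ULN for ALT, AST and ALK-P, ≥2 mg/dL for total bilirubin, and <0.5 × 10^9/L for lymphocytes. Against the other outputs:

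- PCS has one threshold for each enzyme; the ULN table also has >5× and >10×ULN.
- PCS has one lymphocyte cut-off; the lymphopenia table spreads subjects over Grades 1 to 4.
- PCS treats each parameter alone; the Hy's Law count needs ALT or AST ≥3×ULN together with bilirubin ≥2×ULN.
- PCS bilirubin is in mg/dL, not a multiple of ULN.
- The PCS rule for unscheduled values covers the treatment period, and its percentages are restricted to subjects who were not PCS at baseline.

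PCS therefore overlaps with these outputs but does not stand in for them.

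**Step 4: illustration (hypothetical subject).** ALT is not PCS at baseline, every scheduled value is below 3×ULN, and one unscheduled value on treatment is 4×ULN. The PCS table counts the subject, since 4 ≥ 3. The >3×ULN row, built on scheduled values, does not, although 4 > 3.

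**Step 5: size.** An undercount would depend on the number of unscheduled samples and on how often one holds a subject's extreme. The SAP gives neither, so no estimate or defensible range follows from it.

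**The case against.** The strongest reply is that the scheduled-only sentence was meant for by-visit tables. It stands close to the sentence that plans summaries by visit, the three general sections limit the exclusion to by-visit statistics, and the PCS rule shows that the authors did not apply scheduled-only everywhere. Neither the lymphopenia table nor the shift numerator has a scheduled-only limit of its own. This may well be the intention. It makes the defect one of unclear scope, not a settled decision to discard extremes. The unclear scope remains, because the text does not say so.

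Second, the information is not lost. Unscheduled PCS values on treatment are counted, all unscheduled results are listed, the PCS listing shows every value of the parameter for an affected subject, and liver injury and lymphopenia are also reported as events of special interest. Subjects who stop early have an ET visit with scheduled laboratory tests. If the bilirubin ULN is at least 1.0 mg/dL (an assumption; the SAP does not give it), a bilirubin of 2×ULN or more also meets the PCS criterion, so both parts of a Hy's Law case could appear in PCS, though not as a joint count. All this limits the consequence but does not put the value into the table built for it.

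Third, the PCS and ULN tables can differ even on identical data: one uses ≥3×ULN and restricts on baseline, the other uses >3×ULN and states no such restriction. This is correct, so disagreement between them is not by itself evidence of the filter. The illustration in the working avoids both differences.

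Fourth, the filters may be settled in the dataset, programming and mock-table documents that Sections 6, 8 and 9 place elsewhere. That is possible, but those documents are not at hand, and they would have to depart from the literal text of Section 3.7.4.

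**Conclusion.** The concern holds as an inconsistency of scope between Section 3.7.4 and Sections 3.1, 6.1 and 7. Read literally, it leaves five worst-value or any-post-baseline laboratory outputs on scheduled draws only. It should be corrected. These are descriptive safety tables, and no efficacy or tolerability comparison changes.

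Three stronger readings are not supported:

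- A reader might infer that unscheduled values are barred from every laboratory summary. They are not: PCS is a laboratory summary and expressly uses them.
- A reader might infer that Sections 3.1, 6.1 and 7 already require unscheduled values in the five outputs. They only do not forbid them. The uses that Sections 3.1 and 7 name are PCS, the listings and, in Section 7, the last post-baseline value.
- A reader might put a size on it, for example one lost Hy's Law case among the 250 subjects randomized per arm. Nothing in the SAP points to such a case, so the contrast would be hypothetical.

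The conclusion rests on the literal reading of Section 3.7.4 and on the absence of an overriding rule in the documents not seen. The remark about few scheduled draws rests on an inferred reading of Table 1; the inconsistency does not depend on it.

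**What to change.** In Section 3.7.4, replace the scheduled-only sentence with wording such as:

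*By-visit summaries of laboratory data use scheduled results only. The PCS, ULN-category, Hy's Law, maximum lymphopenia grade, shift, and maximum/minimum-change analyses use all post-baseline results in their stated period, whether scheduled, unscheduled or repeat.*

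Two details belong with it. Section 3.7.4 gives a period for the PCS and shift analyses but not for the ULN categories, the Hy's Law count, the lymphopenia grade or the boxplots, so that period should be added. Repeats should be named because Section 6.1 keeps one value per scheduled visit, and a reader could otherwise apply that rule to subject extremes.

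The new wording is compatible with Sections 3.1, 6.1 and 7 but adds a rule that they do not contain; a cross-reference from Sections 3.1 and 7 would keep the three in line. The cost is a short text change and a different data filter, on data already collected and listed. The downside is that counts of abnormal values may rise slightly.

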3.7.5. Vital Signs and ECG

3.7.5.1. Vital Signs

Vital signs for each visit during the entire study will be summarized by treatment group and overall. All vital sign data will be presented in the subject data listings.

Number and percentage of subjects with vital sign values considered PCS occurring at any post-baseline visit will be summarized by treatment group and overall. Criteria for PCS are presented in [Table 3](#) and will be presented for each parameter. The percentages will be calculated relative to the number of subjects with non-PCS baseline values with respect to the specific criterion and at least 1 post-baseline assessment. A supportive listing will present all values for a parameter for subjects with at least one PCS value for that parameter.

In addition, the figure of mean change from baseline along with the corresponding SE will be summarized by visit and treatment group and overall for systolic blood pressure, diastolic blood pressure, and heart rate.

Table 3: Potentially Clinically Significant (PCS) Criteria for Vital Signs

Parameter	Criteria
Systolic Blood Pressure	Low: ≤ 90 mm Hg and decrease ≥ 20 mm Hg High: ≥ 180 mm Hg and increase ≥ 20 mm Hg
Diastolic Blood Pressure	Low: ≤ 50 mm Hg and decrease ≥ 15 mm Hg High: ≥ 105 mm Hg and increase ≥ 15 mm Hg
Pulse Rate	Low: ≤ 50 mm bpm and decrease ≥ 15 bpm High: ≥ 120 mm bpm and increase ≥ 15 bpm

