3.7.5.2. Electrocardiograms

ECG parameters (heart rate, RR interval, PR interval, QRS interval, QT interval, QTcB [QT interval corrected using Bazett's method], QTcF [QT interval corrected using Fridericia's method]) will be summarized for each visit during the study by treatment group and overall.

Number and percentage of subjects with QTcF parameter values considered PCS occurring at any post-baseline visit will be summarized by treatment group and overall. Criteria for PCS are presented in [Table 4](#) and will be presented for each parameter. A subject will be counted only once in the highest category for a given parameter based on the largest post-baseline value. The percentages will be calculated relative to the number of subjects with baseline value ≤ 450 msec and at least 1 post-baseline assessment in the safety analysis set.

A supportive listing will present all values for a parameter for subjects with at least one PCS value for that parameter.

Table 4: Potentially Clinically Significant (PCS) Criteria for QTcF

Parameter	Criteria
QTcF	>450 to ≤ 480 msec

Parameter	Criteria
	>480 to \leq 500 msec
	>500 msec
	Change from baseline >30 to \leq 60 msec
	Change from baseline >60 msec

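### SAP Section 3.7.4 gives two contradictory denominators for the laboratory PCS percentages, and the second admits only subjects who had the event

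*SAP*

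**What the plan says.** SAP Section 3.7.4 calls for a summary of the "number and percentage of subjects with values considered potentially clinically significant (PCS) occurring at any post-baseline visit for selected parameters". It then describes the base of the percentage twice, in consecutive sentences:

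- First sentence: percentages are relative to the "number of subjects with available non-PCS baseline values with respect to the specific criterion and at least 1 post-baseline assessment".
- Second sentence: this one labels a different set as the denominator, namely "total number of subjects with a non-PCS baseline value with respect to the specific criterion and at least 1 postbaseline PCS value".

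The parallel safety rules in the same SAP give one denominator each:

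- Vital signs (Section 3.7.5.1): the "number of subjects with non-PCS baseline values with respect to the specific criterion and at least 1 post-baseline assessment".
- QTcF (Section 3.7.5.2): subjects with a baseline value of at most 450 "msec and at least 1 post-baseline assessment in the safety analysis set".

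Section 3.7.4 also defines the shift-table percentages. For shifts to low, "the numerator is defined as the number of subjects with a post-baseline result below the LLRR"; for shifts to high, "the numerator is defined as the number of subjects with a post-baseline result above the ULRR". The denominators are subjects whose baseline was normal or high (for shifts to low) or normal or low (for shifts to high).

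**The concern.** The two PCS sentences describe different sets. The second set is the part of the first that went on to have the event, so using it as a denominator makes the outcome a condition of entry. The resulting ratio neither estimates a risk nor allows the arms to be compared.

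The faulty sentence is the one that uses the word denominator, so it reads as the operative definition. Two programmers could each follow the SAP and produce different tables. The rule covers every laboratory parameter in Table 2, including ALT, AST, lymphocytes, creatinine and urinary beta-2 microglobulin. Several of these bear on liver injury, lymphopenia and renal injury, which Section 3.7.3 lists as special-interest categories.

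A secondary point concerns the shift tables. Their numerators, as worded, do not exclude subjects already abnormal in that direction at baseline, although the denominators do. The denominators also do not require a post-baseline value. Counting subjects already abnormal would inflate the percentage; including subjects with no post-baseline value would dilute it.

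**Working it through.** The SAP states no PCS rate, so there is no figure of its own to reproduce. The check is on the definitions, with an illustration.

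**Inputs**

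- Arm size: 60 (Part A) + 190 (Part B) = 250 per arm, as planned in SAP Section 2.
- Assumed: *b* = 4 subjects per arm PCS at baseline and still PCS afterwards (range 2 to 8).
- Assumed: *x* = 5 new PCS subjects in one arm and 15 in the other.
- Assumed for the PCS example: every subject has a post-baseline assessment.

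**PCS percentage**

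Let D = 250 − *b* be the subjects not PCS at baseline.

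| Rule | Formula | Arm with 5 new | Arm with 15 new |
|---|---|---|---|
| First sentence | *x*/D | 5/246 = 2.0% | 15/246 = 6.1% |
| Second sentence, numerator limited to non-PCS baseline | *x*/*x* | 5/5 = 100% | 15/15 = 100% |
| Second sentence, numerator as worded (any post-baseline PCS) | (*x* + *b*)/*x* | 9/5 = 180% | 19/15 = 127% |

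The *x*/*x* result does not depend on the assumed counts: it is 100% for any *x* above zero, and 0/0 when *x* = 0. The undefined case would be common for rare criteria. The chance of no event among 250 subjects is (1 − p)^250, which is 0.78, 0.29 and 0.08 for assumed risks of 0.1%, 0.5% and 1%.

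The last row needs the numerator to be read literally, without a baseline restriction. It then exceeds 100% and puts the arm with fewer new events higher. With *b* = 2 it gives 7/5 = 140% versus 17/15 = 113%; with *b* = 8, 13/5 = 260% versus 23/15 = 153%.

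**Shift to low (secondary)**

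Assume 20 subjects newly low, and L subjects low at baseline and still low.

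| L | Numerator as worded, (L + 20)/(250 − L) | Restricted numerator, 20/(250 − L) |
|---|---|---|
| 5 | 25/245 = 10.2% | 20/245 = 8.2% |
| 10 | 30/240 = 12.5% | 20/240 = 8.3% |
| 25 | 45/225 = 20.0% | 20/225 = 8.9% |

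If 12 denominator subjects have no post-baseline value, removing them at L = 10 gives 20/228 = 8.8% instead of 8.3%.

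**Does another section settle it?** No. Section 5 reports no changes from the protocol, and Section 7 restates general summary conventions without a PCS denominator. Sections 3.7.5.1 and 3.7.5.2 support the first laboratory sentence but do not govern laboratory data.

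**The case against.** The strongest reply is that this is a one-word slip whose intent is plain. The second sentence describes exactly the event set of the first, so denominator was very probably written for numerator. The sentence before it supplies a workable denominator, and the vital signs and QTcF rules agree. A table with 100% or 0/0 in every cell would be noticed at once, and the separate programming specifications and mock tables may already have it right. This is probably correct about intent, but it is an inference. Those separate documents are not at hand, and the SAP is the text that has to be right.

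The consequence is also limited, and that stands. Only descriptive safety tables are affected. Subject counts and the PCS listing remain, as do the liver categories by multiple of ULN, the Hy's Law count and the lymphopenia output ("Number of Subjects with Lymphopenia by Maximum NCI-CTCAE Toxicity Grade 1-4 will be summarized").

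The above-100% figures combine two unfavourable readings. Percentages described as relative to a set normally imply a numerator drawn from that set. Those figures are therefore conditional, and the conclusion does not rest on them.

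On the shift tables, the lead-in to each bullet already names the baseline categories, so a subject low throughout has not shifted in the ordinary sense. That makes this a wording clarification. The explicit numerator still omits the restriction.

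**Conclusion.** The concern holds. Section 3.7.4 contradicts itself on the laboratory PCS denominator, and the second sentence cannot serve as one. If it is programmed, the percentage column is 100% or undefined for every Table 2 parameter, whatever the true rates. In the illustration, 2.0% versus 6.1% becomes 100% versus 100%. The event counts are assumed, but the collapse to *x*/*x* follows from the definition alone, provided the numerator is limited to subjects not PCS at baseline and covers the same time window as the denominator. Without the baseline limit the ratio can exceed 100%.

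The correction should be made before the tables are programmed. It affects descriptive safety output only; the primary and secondary endpoints are untouched. The shift-table point is secondary: in the assumed examples the literal numerator gives 10.2% to 20.0% where the restricted one gives 8.2% to 8.9%.

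**What to change.** In Section 3.7.4, delete the second denominator sentence, or relabel it along these lines: *The numerator is the number of subjects with a non-PCS baseline value for the criterion and at least one post-baseline PCS value.* Relabelling is preferable, because it also states the baseline restriction that the numerator now lacks. Keep the first sentence as the only denominator, in line with Section 3.7.5.1.

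In the two shift bullets, state that each numerator counts only subjects in its own denominator (baseline normal or high for shifts to low, baseline normal or low for shifts to high). Also require at least one post-baseline value for entry to the denominator.

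The cost is a few words in the SAP, carried into the programming specifications. No new data are needed.

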2. SAMPLE SIZE AND STATISTICAL POWER CONSIDERATION

Sample Size Considerations (Part A and Part B): The sample size calculation for Part B is based on the secondary endpoint of the mean number of days with any IGISIS individual symptom intensity score ≥ 2 .

Assuming the mean number of days with any IGISIS individual symptom intensity score ≥ 2 is 3.5 and 2.0 for the DMF and ALKS 8700 treatment groups, respectively, a sample size of 500, including 60 randomized subjects per group (120 subjects in total) in Part A and 190 randomized subjects per group (380 subjects in total) in Part B, will provide at least 80% power to detect about a 42% reduction in the number of days with any IGISIS individual symptom intensity score ≥ 2 for the ALKS 8700 treatment group relative to the DMF treatment group, at an alpha level of 0.05 (two-sided) using a negative binomial regression approach. The sample size calculation assumes a standard deviation of 5.9 in the number of days with any IGISIS individual symptom intensity score ≥ 2 relative to exposure days for the DMF treatment group in Part A and Part B.

Assuming the mean number of days with any IGISIS individual symptom intensity score ≥ 2 is 3.5 and 2.0 for the DMF and ALKS 8700 treatment groups, respectively, a sample size of 380 randomized subjects (190 subjects per treatment group) in Part B will provide at least 80% power to detect about a 42% reduction in the number of days with any IGISIS individual symptom intensity score ≥ 2 for the ALKS 8700 treatment group relative to the DMF treatment group, at an alpha level of 0.05 (two-sided) using a negative binomial regression approach. The sample size calculation assumes a standard deviation of 5.9 in the number of days with any IGISIS individual symptom intensity score ≥ 2 relative to exposure days for the DMF treatment group in Part B.

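### As written, the laboratory shift percentages in SAP Section 3.7.4 do not nest the numerator within the denominator, and neither is tied to having a treatment-period value

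*SAP*

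**What the plan says.** SAP Section 3.7.4 announces shift tables for chemistry and hematology by treatment group and overall, and sets their period: "shift from within normal reference limits / low to high during the treatment period will be provided for chemistry and hematology parameters". It then defines the percentages in two bullets.

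- **Shift to low.** The bullet opens "For the shifts from within normal reference limits / high to low". What it counts on top depends only on the later result: "the numerator is defined as the number of subjects with a post-baseline result below the LLRR". What it divides by depends only on the starting value: "the denominator is defined as the number of subjects with a baseline value within the limits or above the ULRR".
- **Shift to high.** The construction is the same with the direction reversed. On top, only the later result matters: "the numerator is defined as the number of subjects with a post-baseline result above the ULRR". Eligibility at the start is again stated for the bottom of the fraction alone: "the denominator is defined as the number of subjects with a baseline value within the limits or below the LLRR".

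The vital-sign rule for potentially clinically significant (PCS) values, in Section 3.7.5.1, is built differently. Its percentages are taken "relative to the number of subjects with non-PCS baseline values with respect to the specific criterion and at least 1 post-baseline assessment". The QTcF rule in Section 3.7.5.2 and the first statement of the laboratory PCS rule in Section 3.7.4 likewise ask for a qualifying baseline and at least one post-baseline assessment.

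**The concern.** A shift percentage should be the share of subjects at risk of the shift who then made it. In these bullets the numerator looks only at the post-baseline result and the denominator only at the baseline value. A subject who is low at baseline and stays low satisfies the numerator wording but is outside the denominator.

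Two further gaps sit in the same bullets:

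- A subject with an eligible baseline and no later sample is in the denominator and can never be in the numerator, so is counted as not shifted.
- A result at the follow-up visit is post-baseline, so it satisfies the numerator wording although the tables are for the treatment period.

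At stake is how the chemistry and hematology shift tables read in the safety evaluation. The first and third gaps push the percentage up and the second pushes it down.

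**Working it through.** The SAP states no figure for these tables, so there is nothing to reproduce. The check sets the wording side by side and then sizes the effect under stated assumptions.

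**Wording**

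| Rule | Baseline condition on numerator | Baseline condition on denominator | Post-baseline value required in denominator | Period of the numerator |
|---|---|---|---|---|
| Shift to low (3.7.4) | none in the definition; implied by the lead-in | within limits or above ULRR | no | post-baseline |
| Shift to high (3.7.4) | none in the definition; implied by the lead-in | within limits or below LLRR | no | post-baseline |
| Vital-sign PCS (3.7.5.1) | – | non-PCS | yes | – |
| QTcF (3.7.5.2) | – | 450 msec or less | yes | – |

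The laboratory PCS rule in 3.7.4 also requires a post-baseline assessment in its first statement. Its next sentence, labelled as the denominator, asks for a post-baseline PCS value and reads like a numerator. Wording in this section therefore cannot safely be left to the programmer's judgement.

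**Gap 1: numerator not nested**

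Inputs:

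- n = 60 + 190 = 250 per arm (Section 2). It gives head counts only and cancels from the percentages.
- b = share abnormal at baseline in the direction of the shift (assumed).
- p = share of those who are still abnormal later (assumed, 0.5 to 0.9).
- q = share of eligible subjects who truly shift (assumed, 5%).

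Formulas:

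- Nested reading: n(1−b)q / [n(1−b)] = q
- Literal reading: [n(1−b)q + nbp] / [n(1−b)] = q + b·p/(1−b)

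Worked case, b = 5%:

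- Eligible: 250 × 0.95 = 237.5. True shifts: 237.5 × 0.05 = 11.875.
- p = 0.5 adds 12.5 × 0.5 = 6.25, giving 18.125/237.5 = 7.6%.
- p = 0.9 adds 12.5 × 0.9 = 11.25, giving 23.125/237.5 = 9.7%.

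| b | Nested | Literal, p = 0.5 | Literal, p = 0.9 |
|---|---|---|---|
| 2% | 5.0% | 6.0% | 6.8% |
| 5% | 5.0% | 7.6% | 9.7% |
| 10% | 5.0% | 10.6% | 15.0% |
| 20% | 5.0% | 17.5% | 27.5% |

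**Gap 2: no post-baseline value required**

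If a share m of eligible subjects has no later sample and q is the rate among those sampled, the stated rule gives q(1−m). The SAP does not give m. With q = 5%, an assumed m of 2% gives 5% × 0.98 = 4.9%, and 10% gives 5% × 0.90 = 4.5%.

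**Gap 3: period**

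Section 3.1 ends the treatment period at the last dose date plus 1 day. Table 1 schedules biochemistry and hematology samples at the follow-up visit as well, which Section 1.2 places 2 weeks after Visit 8 for subjects not entering the long-term study. A subject whose only out-of-range value is at that visit meets the numerator wording. The SAP gives nothing from which to size this.

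**The case against.** The strongest reply is that the lead-in settles the matter. What follows the colon concerns shifts from normal or high to low, and a subject who was low throughout has made no such shift. On that reading the inflation in gap 1 is zero. The programming specifications and mock tables are separate documents (Sections 8 and 9) and may already say so. This carries real weight: a nested numerator was probably intended. But the words after the colon are the operative definitions, the baseline condition is spelled out for the denominator and omitted for the numerator, and nothing else in the SAP states the nesting.

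On gap 2, Section 6.3 says laboratory analyses use observed data without imputation, and early discontinuers return for Visit 8, where laboratory samples are scheduled. Few subjects should lack a value, so the effect is likely small. Still, the denominator as defined does not remove them, and the parallel rules do. The lead-in answers neither gap 2 nor gap 3.

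A reader might infer more than the document supports:

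- **That carried-in abnormality will be reported as an on-treatment shift.** This is a risk of literal programming, not an established result.
- **That percentages will exceed 100%.** With q = 5% and p = 0.9, this needs 0.05 + 0.9b/(1−b) > 1, that is b > 0.95/1.85, about 51% of subjects abnormal at baseline. Nothing in the SAP suggests that.
- **That a false treatment difference will appear.** With equal b and p the added amount is the same in both arms. A gap needs a baseline imbalance, which randomisation makes zero on average, and the SAP gives no baseline laboratory rates.

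Lymphopenia grades, liver-enzyme multiples of ULN, Hy's Law counts, change from baseline and full listings are also planned in Section 3.7.4. They would help to expose a misleading shift percentage.

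**Conclusion.** Wrong as written, minor. The shift percentages are not explicitly nested, the denominator does not require a post-baseline value, and the numerator is not limited to the period that the tables are meant to cover. The first gap is probably a drafting slip. The other two remain even on the generous reading.

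The size of the first gap, if programmed literally, is b·p/(1−b). The values of b, p and q used above, and of m in the second gap, are all assumptions, so the results illustrate the mechanism and do not forecast the tables. The effect is confined to descriptive safety tables. The primary and secondary endpoints, and any test or superiority claim, are untouched.

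**What to change.** Reword the two bullets in Section 3.7.4:

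- **Shift to low.** Denominator: subjects whose baseline value is within limits or above the ULRR and who have at least one treatment-period value for that parameter. Numerator: subjects in that denominator with at least one treatment-period value below the LLRR.
- **Shift to high.** Denominator: subjects whose baseline value is within limits or below the LLRR and who have at least one treatment-period value. Numerator: subjects in that denominator with at least one treatment-period value above the ULRR.

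Use the treatment-period definition in Section 3.1, show the denominator count for each parameter, and carry the same wording into the programming specifications. The cost is two sentences, with no new data or analyses. One consequence should be visible in the table: a subject whose only later sample falls after the last dose date plus 1 day leaves the denominator, so the number excluded for that reason should be footnoted.
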